### 6.3.2 Power Considerations

Because there is no evidence that a home-based, computerized CT program will be feasible for this population and in multiple COG institutions, our primary aims are to evaluate the program's ease of use and participant compliance, which we will define as 80% of sessions completed within 9 weeks of starting treatment. The goal is to have at least 75% of participants being compliant (i.e., completing 20 or more of the 25 sessions). Randomized patients who are removed off protocol therapy for medical reasons (relapse/progression, death, physician's determination in the patient's best interest, development of seizures or other change in functional status, or starting or changing the dose of psychostimulants) would be deemed inevaluable for the primary compliance endpoint. With 60 evaluable participants, if the true compliance rate in the study participants is 59%, the power to detect such decrease from the target 75% compliance rate is 0.82. Power consideration is based on a Z-test for binomial proportion with continuity correction at 1-sided level of 0.05.

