## 6.2 Patient Accrual and Expected Duration of Trial

The study accrual target is 60 randomized patients evaluable for the primary endpoint of intervention compliance. It is anticipated that some children who complete the baseline assessment will not meet the eligibility criteria for randomization based on evidence of intellectual disability or psychiatric functioning. In the trial of *Cogmed* with survivors, less than 10% of children screened were excluded from participation for these reasons.

Randomized patients who are removed off protocol therapy for medical reasons (relapse/progression, death, physician's determination in the patient's best interest, development of seizures or other change in functional status, or starting or changing the dose of psychostimulants) would be deemed inevaluable for the primary compliance endpoint. Therefore, using an estimate of 15% for screen failures and inevaluable patients, we project that we may need to enroll up to 71 participants.

With enrollment open to all institutions within COG, we anticipate that our goal of accruing 60 evaluable patients from those eligible is feasible within two years after Amendment #1 is activated. There are very few on-therapy cognitive intervention trials from which to base an estimate of feasibility, though at St. Jude Children's Research Hospital, recruitment to SJMB03, which has a reading-based intervention program embedded in the study, was strong. Specifically, 64% of children enrolled on the protocol have been randomized to either the treatment or standard-of-care arm of that protocol. The primary reasons that children were not randomized, in order of frequency, included 1) age outside the inclusion criteria, 2) poor medical status (including posterior fossa syndrome), 3) non-English speaking, and 4) parents did not consent to randomization ([name], study PI, personal communication on Oct. 29, 2010). We anticipate that parents of children receiving cranial radiation therapy will be aware of the potential risks of neurocognitive late effects, and that at least one quarter of these parents will be willing to have their children participate in a cognitive intervention trial, particularly since it is home-based. The project has the strong support of the Behavioral Sciences Committee, and we have identified key personnel at each site who can help to inform colleagues about the study and motivate referrals of eligible patients.

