### 6.3.3 Analysis Plan

Compliance rate (the portion of patients who complete at least 80% of the sessions within 9 weeks) will be calculated for the overall study population and each arm separately. Z-test for binomial proportion with continuity correction will be used to examine if the overall compliance rate is lower than the target of 75%. Confidence intervals of the estimated compliance rate will be constructed for the overall study population and for each arm separately. We will use Fisher's exact test to examine if there is any significant difference in the compliance rate between the 2 arms. Compliance data on the number of sessions completed for all patients and for patients on each arm will also be described by summary statistics such as mean or median, and compared between the 2 arms by two-sample t-test or Wilcoxon rank sum test. We will use descriptive and summary statistics to report parent and child ratings of the intervention's technical feasibility, ease-of-use, and satisfaction across the three time-points that this information is collected. In addition, we will use descriptive and summary statistics to detail the total number of patients enrolled, determine rates and reasons for non-eligibility and patient refusal for randomization, characterize socioeconomic status of the parents and computer usage for the patients and evaluate the number and type of adverse incidents reported through the questionnaires (if any). We will use a series of t-tests (for continuous variables) and Chi-square tests or Fisher's exact tests (for non-continuous variables) to examine potential differences between eligible patients who accept or decline to be randomized to the treatment phase, between participants who are compliant (i.e., 80% of sessions completed) and noncompliant, and for other medical, psychosocial, and contextual factors.

The analysis of preliminary efficacy will be conducted on an intent-to-treat basis. We will use descriptive/summary statistics to summarize the objective and the subjective measures of attention and WM in each arm and the differences between the 2 arms on the post-intervention/6-month assessment or on the difference between the post-intervention/6-month assessment and the baseline assessment. Linear regression models using the post-intervention/6-month assessment as outcome will also be used to estimate the effect size of intervention with adjustment for potential confounders including the baseline assessment. Linear

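### Section 6.3.2 gives power of 0.82 at 60 evaluable patients; the planned test rejects there only at 38 or fewer compliant, so its power at 59% is 0.79

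*Combined protocol and SAP*

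**What the plan says.** Section 6.3.1 defines compliance as at least 20 of the 25 sessions completed within 9 weeks, with a target of at least 75% of participants compliant. Section 6.3.2 takes 60 evaluable participants and a true rate of 59% and states that "the power to detect such decrease from the target 75% compliance rate is 0.82". It names the method: "Power consideration is based on a Z-test for binomial proportion with continuity correction at 1-sided level of 0.05".

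Section 6.3.3 plans the same test for the analysis, asking whether the overall rate lies below 75%. It adds estimation: "Confidence intervals of the estimated compliance rate will be constructed for the overall study population and for each arm separately".

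The number 60 is the recruitment goal as well as the planning figure. Section 6.2 says "The study accrual target is 60 randomized patients evaluable for the primary endpoint of intervention compliance", and after an allowance of 15% for screen failures and inevaluable patients, "we project that we may need to enroll up to 71 participants". No section prints the number of compliant patients at or below which the test rejects.

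**The concern.** The figure of 0.82 is the only power statement in the plan, and it concerns the primary endpoint. It treats the rejection boundary as a point on a continuous scale, whereas the test can only act on whole patients. With 60 patients the boundary falls just short of 39, so the formula credits almost the whole step from 38 to 39, and the test cannot use that step.

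Two things are at stake. The chance of missing a true rate of 59% is understated. And because the cut-off is not printed, a reader cannot see at once that 39 of 60 (65%) would not be declared below 75%, a result that misses the 0.05 level by only 0.0005.

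**Working it through.** **Inputs.** n = 60, alternative rate 0.59, one-sided level 0.05 and continuity-corrected Z-test (section 6.3.2); null rate 0.75 (sections 6.3.1 to 6.3.3); lower-tail test of the overall rate (section 6.3.3). The normal quantile is 1.645.

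**1. Reproducing the stated figure.**

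- Boundary as a count: 60 × 0.75 − 0.5 − 1.645 × √(60 × 0.75 × 0.25) = 45 − 0.5 − 1.645 × 3.354 = 38.98, or 0.6497 as a proportion.
- Power: Φ[(0.6497 − 0.59) / √(0.59 × 0.41 / 60)] = Φ(0.0597 / 0.0635) = 0.8265.

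This agrees with 0.82 to within 0.01. The same formula gives 0.858 without the continuity correction and 0.746 if two-sided, so the one-sided corrected form is clearly the one used.

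**2. Where the test rejects at n = 60.** The statistic is z = (x + 0.5 − 45) / 3.354, and the test rejects if z ≤ −1.645.

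| Compliant, x | z | one-sided p | Reject? |
|---|---|---|---|
| 38 (63.3%) | −1.938 | 0.0263 | yes |
| 39 (65.0%) | −1.640 | 0.0505 | no |

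The cut-off does not depend on how the test is coded. With the observed-rate standard error, p is 0.041 at 38 and 0.068 at 39. With an exact binomial test, p is 0.0298 at 38 and 0.0541 at 39. All three reject at 38 or fewer.

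**3. Operating characteristics of that rule.**

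- Power at 59%: P(X ≤ 38 | 60, 0.59) = 0.791.
- Size at 75%: P(X ≤ 38 | 60, 0.75) = 0.030.
- A cut-off of 39 would give power 0.859, but exact size 0.054.

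**4. Whether this is only exact versus approximate.** It is not. The normal approximation at the cut-off the test can attain, with the continuity correction, is Φ[(38.5 − 60 × 0.59) / √(60 × 0.59 × 0.41)] = Φ(3.1 / 3.81) = 0.792. The two methods agree once the cut-off is a whole number.

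**5. Sensitivity to the evaluable number.** The same rule at nearby n:

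| n | Cut-off | Exact power at 59% | Normal approximation | Exact size |
|---|---|---|---|---|
| 57 | 36 | 0.779 | 0.809 | 0.032 |
| 58 | 37 | 0.809 | 0.815 | 0.038 |
| 59 | 38 | 0.836 | 0.821 | 0.046 |
| 60 | 38 | 0.791 | 0.827 | 0.030 |
| 61 | 39 | 0.819 | 0.832 | 0.036 |
| 62 | 40 | 0.844 | 0.838 | 0.043 |
| 63 | 41 | 0.867 | 0.843 | 0.051 |
| 64 | 41 | 0.829 | 0.848 | 0.034 |

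Exact power is at least 0.819 for every n from 61 to 71.

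**6. Sensitivity to the alternative.** At n = 60, exact power reaches 0.80 at a true rate of 58.8% and 0.82 at 58.3%; it is 0.83 at 58%.

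**The case against.** The best case for leaving the text alone is that 0.82 is a correctly labelled planning approximation. Section 6.3.2 names the Z-test and claims no exact binomial power, and ignoring the whole-number cut-off is part of what the standard formula does. Sixty is also an unlucky number: exact power is higher at 58, 59, 61 and 62, and its average over n = 58 to 62 is (0.809 + 0.836 + 0.791 + 0.819 + 0.844) / 5 = 0.820. The final evaluable number depends on events after randomization and may well not be 60. The 59% alternative is given without derivation, and lowering it by 0.7 of a percentage point closes the gap. The cut-off follows mechanically from the stated test and level, and the planned confidence interval would show the uncertainty around a result such as 39 of 60.

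All of this is true, and it is why the point is minor. What it does not remove is that section 6.3.2 attaches 0.82 to exactly 60 evaluable patients, the number that section 6.2 sets as the target, and for the test planned in section 6.3.3 the power at that number is 0.79. As a description of the design in the neighbourhood of 60, 0.82 is fair; as a statement about 60, it is too high.

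**Conclusion.** The point holds, at low severity. With 60 evaluable patients the planned test has power 0.791 against a true rate of 59%, 2.9 points below the stated 0.82. The type II error is about 21% (1 − 0.791) and not 18% (1 − 0.82). The exact one-sided size is 0.030, so the test at 60 is conservative. The cause is discreteness, not faulty arithmetic.

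The result assumes exactly 60 evaluable patients, independent outcomes with a common compliance rate, and the level of 0.05 applied strictly, so that p = 0.0505 does not reject. With a different evaluable number the gap can shrink or reverse. No decision about sample size, test or level turns on it.

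**What to change.** Replace the power sentence in section 6.3.2 with wording such as:

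> With 60 evaluable participants the test rejects at 38 or fewer compliant; exact power is 0.79 at a true rate of 59% (0.83 at 58%) and exact one-sided size is 0.03. The cut-off will be recomputed by the same rule if the evaluable number differs from 60.

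The cost is one sentence and a stated power about 3 points less favourable. If the cut-off is recomputed by the same rule, exact size stays at or below 0.05 for every n from 57 to 71 except 63 (0.051) and 70 (0.052), a negligible excess. Printing the cut-off in advance also settles how a borderline 39 of 60 would be read.

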### 6.3.3 Analysis Plan

Compliance rate (the portion of patients who complete at least 80% of the sessions within 9 weeks) will be calculated for the overall study population and each arm separately. Z-test for binomial proportion with continuity correction will be used to examine if the overall compliance rate is lower than the target of 75%. Confidence intervals of the estimated compliance rate will be constructed for the overall study population and for each arm separately. We will use Fisher's exact test to examine if there is any significant difference in the compliance rate between the 2 arms. Compliance data on the number of sessions completed for all patients and for patients on each arm will also be described by summary statistics such as mean or median, and compared between the 2 arms by two-sample t-test or Wilcoxon rank sum test. We will use descriptive and summary statistics to report parent and child ratings of the intervention's technical feasibility, ease-of-use, and satisfaction across the three time-points that this information is collected. In addition, we will use descriptive and summary statistics to detail the total number of patients enrolled, determine rates and reasons for non-eligibility and patient refusal for randomization, characterize socioeconomic status of the parents and computer usage for the patients and evaluate the number and type of adverse incidents reported through the questionnaires (if any). We will use a series of t-tests (for continuous variables) and Chi-square tests or Fisher's exact tests (for non-continuous variables) to examine potential differences between eligible patients who accept or decline to be randomized to the treatment phase, between participants who are compliant (i.e., 80% of sessions completed) and noncompliant, and for other medical, psychosocial, and contextual factors.

The analysis of preliminary efficacy will be conducted on an intent-to-treat basis. We will use descriptive/summary statistics to summarize the objective and the subjective measures of attention and WM in each arm and the differences between the 2 arms on the post-intervention/6-month assessment or on the difference between the post-intervention/6-month assessment and the baseline assessment. Linear regression models using the post-intervention/6-month assessment as outcome will also be used to estimate the effect size of intervention with adjustment for potential confounders including the baseline assessment. Linear

mixed model analyses which include measures at all time-points will also be considered to examine and estimate the effect size of the intervention with adjustment for within-patient dependence of the measures over time. We will also explore in various regression models which medical, psychosocial, and environmental factors are related to feasibility, acceptability, and short-term efficacy of the intervention. In particular, age of the participants and socioeconomic status measures which are potentially important predictors will be examined in these models.

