Participants meeting criteria for randomization will be trained in the use of the *Cogmed* programs in the clinic by study personnel (see below and [Appendix II](#)). In order to avoid biasing the sample towards socioeconomically advantaged individuals, participants without dedicated access to an adequate home computer will be provided with a laptop computer or tablet device for the duration of the intervention, regardless of whether they are assigned to the adaptive or non-adaptive arms. Moreover, families without available internet access will be provided with wireless internet cards for the duration of the intervention. The intervention will consist of three to five, 15- to 45-minute sessions (younger children practice for less time) per week for 5 to 9 weeks (total = 25 sessions). If patients do not complete the training within 9 weeks, they will be removed off protocol therapy but will remain on study and will receive the post-intervention and follow-up assessment. Similarly, patients who do not complete the 25 sessions for any reason will receive the post-intervention and follow-up assessment unless they meet Off Study Criteria (see [Section 5.0](#) below). Thus, using an intent-to-treat approach, every effort will be made to obtain post-intervention and follow-up data on every child who is randomized, unless they meet Off Study Criteria.

To assist participants as they complete the intervention, a treatment “coach” will be available to parents and children by phone throughout the intervention period. Weekly phone contact with the coaches will be scheduled so that compliance and feasibility data may be collected and so that any problems (e.g., training issues, adverse events, technical problems) can be addressed efficiently. Of note, *Cogmed* routinely provides technical assistance to individuals using the programs at no additional cost. Additionally, to promote compliance and maintain children’s interest in the program, participants will earn \$10 gift cards (or comparably valued prizes/compensation) after completion of approximately each third of the training (total = \$30). This incentive schedule is similar to the one used in the trial of this program in survivors of childhood cancer, and was associated with a compliance rate of 85%.

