### 5.0 CRITERIA FOR REMOVAL FROM PROTOCOL THERAPY AND OFF STUDY CRITERIA

#### 5.1 Criteria for Removal from Protocol Therapy

- a) Refusal of further protocol treatment by patient/parent/guardian.
- b) Completion of planned study treatment.
- c) Physician determines it is in patient's best interest.
- d) Patient does not complete the computerized cognitive training within 9 weeks.
- e) Development of seizures or change in functional status that will prevent patient from completing further treatment or assessments.
- f) Progressive disease or relapse

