##### 7.1 CDUS

This study will be monitored by the Clinical Data Update System (CDUS) Version 3.0. Cumulative protocol- and patient-specific CDUS data will be submitted quarterly to CTEP by electronic means. Reports are due January 31, April 30, July 31 and October 31. CDUS reporting is not a responsibility of institutions participating in this trial.

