In each version of the intervention, children complete 25 training sessions. Children are asked to complete between 3 and 5 sessions per week, so the total treatment time to complete 25 sessions may range from 5 to 9 weeks. For children completing *Cogmed RM*, sessions typically last between 25 and 45 minutes, depending on the child's working memory span. For younger children completing *Cogmed JM*, sessions are designed to be shorter in accordance with young children's cognitive stamina; thus, younger children's training sessions typically last about 15 minutes.

Throughout training, the child's intervention coach has online access to detailed information about his or her training sessions. Specifically, coaches can see when and how long children trained, and the outcome (pass or fail) of each of the trials children complete during a single training session. Using this information, coaches can modify the training sequence or make suggestions to the child and/or parent about how progress can be maximized (e.g., by taking a short break after three failed trials to prevent frustration). Families will have phone meetings at least once per week with an intervention coach to ensure compliance, track progress, provide feedback and answer any questions that may have arisen during treatment. Coaches will also have an assessment script for these calls, for re-evaluating medical, psychological, and environmental factors that may potentially be related to feasibility and efficacy of the intervention.

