***Satisfaction / Ease of use:***

1. Using the following scale, how easy or difficult was it for your child to use the computer to do the exercises in the following areas?

very easy    somewhat easy    neither easy/hard    somewhat hard    very hard

a. turning on/logging in: \_\_\_\_\_

b. starting the program: \_\_\_\_\_

c. using the mouse: \_\_\_\_\_

2. Using the following scale, how easy or difficult was it for your child to do the exercises?

very easy    somewhat easy    neither easy/hard    somewhat hard    very hard

3. Using the following scale, how often were you present with your child while s/he was doing the exercises?

Never    Rarely    Sometimes    Often    Always

4. Using the following scale, how often did your child experience physical pain or discomfort while using the computer program?

Never    Rarely    Sometimes    Often    Always

If any response other than "never": Please describe the physical pain or discomfort your child experienced: \_\_\_\_\_

---

---

5. Using the following scale, how often did your child experience frustration while using the computer program?

Never    Rarely    Sometimes    Often    Always

6. Using the following scale, how often did your child feel bored during the computer exercises?

Never            Rarely            Sometimes            Often            Always

7. Using the following scale, how often did your child enjoy completing the exercises?

Never            Rarely            Sometimes            Often            Always

8. Using the following scale, how satisfied were you with your child's participation in the study this month?

Very dissatisfied    Somewhat dissatisfied    Neither    Somewhat satisfied    Very Satisfied

Other comments or concerns: \_\_\_\_\_

---

---

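### Section 6.3.3 takes adverse incidents only from the questionnaires and not by arm, so events raised on coach calls and removals for seizure have no planned summary

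*Combined protocol and SAP*

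**What the plan says.** Section 6.3.3 lists, among its descriptive outputs, that it will "evaluate the number and type of adverse incidents reported through the questionnaires (if any"). It names no other source for incidents and no split by arm. Compliance, in the same section, is to be reported overall and by arm and compared between arms.

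Elsewhere the protocol describes other routes by which harm becomes known:

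- Section 4.3 schedules weekly coach calls so that "any problems (e.g., training issues, adverse events, technical problems) can be addressed efficiently".
- Appendix II adds: "Coaches will also have an assessment script for these calls, for re-evaluating medical, psychological, and environmental factors". It ties these factors to feasibility and efficacy, not to an incident count.
- Section 5.1(e) ends protocol therapy for "Development of seizures or change in functional status that will prevent patient from completing further treatment or assessments".
- Sections 6.2 and 6.3.2 say that randomized patients removed for medical reasons, seizures included, "would be deemed inevaluable for the primary compliance endpoint".

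On reasons, section 6.3.3 will "determine rates and reasons for non-eligibility and patient refusal for randomization". Reasons for removal after randomization are not listed.

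**The concern.** The source rule is narrower than the trial's own channels. The only contact at which the protocol expressly expects adverse events to come up is the coach call, and calls do not feed the count. A child removed for a seizure leaves the primary analysis and appears in no planned table of removal reasons.

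The Abstract and section 2.4 describe the training as free of recognised harms, and section 2.0 says the results will be pilot data for a larger randomized trial. A low incident count would be read as support for the first statement and carried into the second. Section 4.1 expects almost all participants to be on chemotherapy, so a pooled count with no reference to the non-adaptive arm would be hard to interpret even if it were complete.

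**Working it through.** The point is mainly one of scope, so the check sets the passages side by side.

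**1. What the questionnaires can pick up.** Under Table 1 and section 4.6, the parent Feasibility Interview is given after session 12 and at post-intervention, and the child interview at post-intervention. (Section 4.5.3 also suggests a parent interview at 6 months; the items would be the same.) The parent's structured tolerability items are "how often did your child experience physical pain or discomfort while using the computer program", plus frustration, boredom and enjoyment. The child's items are frustration, boredom and enjoyment, with space for comments. No item asks about seizures. One could be reported in the parent's comment field or in answer to the open questions at post-intervention, such as the one on the greatest difficulties in completing training. The BASC-3 and BIS are baseline only. The BRIEF is repeated, but it measures executive function.

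**2. Who may lack questionnaire data.** A child removed before session 12 does not reach that interview. Under section 4.3, children removed from therapy still receive the post-intervention assessment unless they meet off-study criteria. Section 5.1(e), however, itself covers children who cannot complete assessments, and a child who starts a psychostimulant goes off study under section 5.2(f).

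**3. Direction of the error.** Let Q, C and R be the sets of distinct incidents known from questionnaires, coach calls and medical removal records.

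- Planned count = |Q|.
- Full count = |Q ∪ C ∪ R| = |Q| + |(C ∪ R) \ Q|.
- The second term is zero or positive, so planned count ≤ full count. They are equal only if every incident in C and R was also given on a questionnaire.

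**4. Size.** The protocol gives no incident rate, so |(C ∪ R) \ Q| cannot be estimated. The one related figure is the enrollment allowance in section 6.2:

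- Enrollment = 60 / (1 − 0.15) = 70.6, rounded up to 71, which reproduces the plan's figure.
- Screen failures and inevaluable patients combined = 71 − 60 = 11.
- The split is not stated. Taking medical removals anywhere from 0 to 11 (an assumption), they make up 0/60 = 0% to 11/71 = 15.5% of randomized patients.

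These removals have several causes, including progression, and need not be adverse incidents. The range shows only how many could leave for medical reasons with no planned table giving the reason by arm.

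**5. Other outlets.** Section 7.1 says "Cumulative protocol- and patient-specific CDUS data will be submitted quarterly to CTEP by electronic means", but describes no adverse-event content or analysis. The case report forms mentioned in section 7.0 are posted elsewhere.

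**The case against.** The strongest reply is that the information is not lost. Medical removal reasons must be recorded to decide who is evaluable. The factors on the coach script closely match those that section 6.3.3 will explore in regression models of feasibility, acceptability and efficacy. The case report forms and the coach script, neither reproduced in the protocol, may collect more. This stands: the gap is in the planned summary, not shown to be in collection. A regression covariate, though, is not an incident count.

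A second reply is that the questionnaires have an advantage. They are structured, the same in both arms, and answered by families blinded at least at first, whereas coaches are unblinded (section 4.1). This also stands. It argues for eliciting events on calls uniformly and stating the limitation, not for leaving calls out.

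Third, the trial has no safety objective and promises only a descriptive count. With about 30 children per arm, a comparison of rare events would say little. That limits the weight of the point, but tabulating by arm needs no test.

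Two stronger readings are tempting. A reader might infer the share of events missed from the number of weekly calls over 5 to 9 weeks against two parent interviews. That compares contacts, not events: the interview items look back over the training, the child interview adds another occasion, and the protocol does not say whether the session-12 interview is part of a coach call. A reader might also infer that a seizure could be reported only by accident. The open question on difficulties at post-intervention is a real, if indirect, prompt.

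**Conclusion.** The point holds as one of scope. Followed as written, section 6.3.3 yields an incident count that can only match or understate what the trial knows, and that cannot be read by arm. Removals for seizure or functional change have no planned table. The direction is certain; the size cannot be derived. The 0 to 11 range rests on an unstated split and bounds medical removals within the allowance, not missed incidents.

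The conclusion assumes that incidents are summarised only as section 6.3.3 states and that no unseen form or report adds a planned table. It does not show that safety data go uncollected, that the coach script lacks particular questions, or that harm would be concealed. The primary compliance analysis is unaffected. This is a modest, inexpensive improvement to the plan.

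**What to change.** In section 6.3.3, replace the questionnaire-only source with wording such as: *The number and type of adverse incidents will be summarised by arm among all randomized patients, from questionnaires, coach calls, and records of removal for seizure or change in functional status, with each event counted once.*

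Add a separate table by arm of reasons for removal from protocol therapy (section 5.1) and of off-study reasons arising after randomization (section 5.2). Keep it apart from the incident count. Completion of training or assessments and disease progression are not adverse incidents, and patients who were never randomized have no arm.

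Have coaches ask about and record incidents in the same way in both arms, and report their unblinded status as a limitation of incidents found by that route.

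The cost is a short amendment to section 6.3.3, consistent recording on calls already scheduled, and slightly more data entry. The reported count may be higher and less favourable. Sample size, power and the removal criteria stay as they are.
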